The use of health information technology (HIT) to provide healthcare at a distance has been described as the single most important way to equalize the differences between rural and urban settings.²⁰ Our pilot study indicated that a new model of transitional care using existing, readily available, video-visit technology is a successful way to communicate with and continue to support FCGs of palliative care patients living in rural areas.^{21,22} Given these promising results and the significant needs of the FCGs in their challenging role of caring for loved ones with life-limiting illnesses, it is critically important that these preliminary findings now be examined in a clinical trial that tests extending transitional care, through the use of video visits. Moreover, reliable assessments of the monetary and time contributions of the FCGs while providing palliative care to their loved ones are lacking due to multiple challenges including the fact that such costs are difficult to obtain and need to be assessed in a prospectively designed randomized control trial to be reliable.^{1,23} Therefore, the purpose of this study is to evaluate a novel, nurse-led, technology-enhanced, theory-based²⁴ care model of transitional palliative care (TPC) for FCGs living in rural, medically underserved areas. The TPC model for FCGs is individualized to improve continuity of care based on evidence-based transitional and palliative care principles by providing ongoing FCG support, enhancing FCGs' knowledge and skills while attending to FCGs' own health needs. We will test the efficacy of this new care model with the following **specific aims**:

Aim 1: To evaluate the effect of technology-enhanced TPC for FCGs on caregiving preparedness, communication with clinicians, and satisfaction with care for FCGs as the care recipient moves from hospital care to home. We hypothesize that FCGs randomized to the intervention will report increased preparedness for caregiving, improved communication with clinicians, and greater satisfaction with care during the study enrollment period compared to FCGs randomized to usual care.

Aim 2: To evaluate the effect of technology-enhanced TPC for FCGs' on quality of life, burden, coping skills, and depression. We hypothesize that FCGs in the intervention group will report increased quality of life and coping and decreased depression and burden during the study enrollment period compared to FCGs randomized to usual care.

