In our proposed study, the nature of the framework involves two salient types of transition: (1) the care recipient's eligibility for, and acceptance of, palliative care due to a life-limiting illness and (2) the transition of the care recipient from the hospital to home. Both of these types of transition have complex patterns. Transition properties include the quality of the FCG-care recipient relationship. Also, caregiving demands during the transition may influence the transition condition. Personal, social, and community transitions can act as either facilitators or barriers. For instance, FCG beliefs about caregiving can have a positive (facilitator) or negative (barrier) impact on caregiver well-being.¹²⁴⁻¹²⁷ Conditions of the transition (as facilitators or inhibitors/barriers) include spiritual/religious beliefs,¹²⁸ time available for caregiving (other FCG responsibilities & demands),¹²⁹ decision-making preference,¹³⁰ health literacy,¹³¹ income, FCG support needs,¹³² readiness for hospital discharge,¹³³ and FCG personal health issues.¹²⁹

In this study the FCG transition process indicators will be measured by FCGs' preparedness for caregiving,¹³⁴ communication skills,¹³⁵ and satisfaction with care (Aim 1).^{136,137} Recognizing the potential effect of caregiving on FCGs' health, we will measure FCGs' quality of life,^{9,138} coping,¹³⁹ depression,¹⁴⁰ and burden¹⁴¹ as transition outcome indicators (Aim 2). The FCGs have a substantial effect on care recipients' overall care and symptom management; therefore, we will in turn evaluate healthcare costs from a societal perspective including costs borne by FCGs and care recipients (Aim 3).^{8,87}

[figure not shown]
Research Design

The RCT design will be used to test the efficacy of technology-enhanced TPC for FCGs on outcomes related to the FCGs' experience and determine the impact on costs from a societal perspective. After informed consent is obtained, FCGs will be randomly assigned to one of two groups by computer-generated randomization lists: 1) the experimental group or 2) a "usual care" or control group. Consistent with transitional care models,^{142,143} the intervention period will continue for 8 weeks after care recipients are discharged from the hospital.

Setting

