Our target population is community-dwelling adult FCGs providing care to a loved one who has a serious life-limiting condition and is new to palliative care, the care recipient will also be consented into the study. A FCG is broadly-defined as the person self-identified as the family member or unpaid friend who is the primary informal caregiver for a patient with a terminal illness. The FCG may or may not be a member of the care recipient's nuclear family. FCGs and their corresponding care recipient will be approached for study enrollment by either members of the palliative care team or the study coordinator (SC) using an IRB-approved informational brochure, including contact information for members of the study team if further discussion is requested, during the care recipients' hospital stays. Alternatively, the study coordinator may call a patient's primary caregiver to introduce the study if the caregiver and the patient meet the criteria for enrollment. Interpreters will be available for individuals who have difficulty with the English language.

FCGs

Inclusion Criteria. Any adult FCG (≥ 21 years of age) of adult patients (≥ 21 years of age) hospitalized at Mayo Clinic Hospital — Rochester, Mayo Clinic Health Systems in Mankato and/or LaCrosse who receives an in-hospital palliative care consult and lives in a Minnesota, Iowa or Wisconsin county that is designated as medically underserved or rural will be invited to participate.

Exclusion Criteria. The FCGs of patients who live in Rochester, MN, will be excluded. Rochester, MN is not considered a medically underserved or rural area.^{144,145} The FCGs of patients with left ventricular assistive devices, documented chronic pain, use of home infusion pain pumps, or documented active addictive behaviors (documentation of FCG's current substance use or treatment in care recipient medical record) will be excluded from this study because of their unique needs in caregiving are not addressed by this study.

Care Recipients

Inclusion Criteria. Any adult patient (≥ 21 years of age) hospitalized at Mayo Clinic Hospital — Rochester, Mayo Clinic Health Systems in Mankato and/or LaCrosse who receives an in-hospital palliative care consult and lives in Minnesota, Iowa or Wisconsin will be invited to participate.

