Upon completion of the informed consent process, the SC will retain documentation of the FCG's consent and the care recipient's consent/assent along with the assessment in the research study files, including the name and job title of the study team member who explained the study, a brief description of what was explained, questions (if any) that were asked and answered, confirmation that the subject expressed understanding of the study and willingness to participate, and the list of written information given to the subject.

Based on recruitment approaches, including introduction of the study by our trained SC and, when possible, by the members of the hospital palliative care consulting service, review of palliative care admission lists by a study coordinator, FCG remuneration, our prior experience enrolling hospice eligible patients while still hospitalized,¹⁴⁶ and flexibility in data collection to meet FCG preferences, we are confident in our ability to recruit the necessary 8 participants per month to meet the subject accrual goals in a timely manner.

Sample Size and Power Calculations

Determination of sample size is based on the analyses of study Aims 1 and 2 to detect a meaningful effect size. The focus of this study is FCGs. With a sample size of 100 FCGs per group, we will have 80% power to detect an effect size 0.487 at an alpha level of 0.01, assuming a two-sided, two-sample t-test is appropriate. This suggests that if a standard deviation of difference between two groups for a particular endpoint is 1 unit, then a difference of 0.487 points per month between two groups for that endpoint will be detectable with this sample size. Given that our primary outcome of interest is rate of change, only FCGs with at least one post-baseline measurement would be able to be evaluated. To account for a possible attrition rate of ~30%,⁹ due to unanticipated events such as loss to follow-up, we plan to recruit a total of 500 FCGs per group at an average of 8 FCGs per month over a planned 36-month enrollment period. We are confident we will enroll the target number of FCGs, as there were over 300 patients seen by the palliative care consulting service in both 2014 and in 2015 and discharged home to the major catchment area of the study setting.

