Aims 1 and 2. Statistical analyses of Aims 1 and 2 will be performed in a similar manner. Every FCG will be evaluated using various scales and survey instruments at baseline, 2 weeks, and 8 weeks post patient discharge (Table 1). We will use a response-feature analysis as our primary approach in analyzing these repeated measures data.¹⁸¹ For each FCG, the magnitude of the scores from the respective instruments will be plotted versus time (measured in months); least squares regression will be used to estimate a participant-specific rate of increase in points per month. This slope parameter estimate will be used as the response feature for each participant and is the primary endpoint for this study. The primary analysis of this endpoint will be analyzed using a two-sample t-test or Wilcoxon rank-sum test, as appropriate. The endpoints will also be analyzed using a fixed-effects linear regression model. This model will use the estimated regression-slope response-feature as the dependent variable and have independent variables consisting of intervention (yes, no) as well as any baseline covariates such as FCGs’ age, employment status, etc. These analyses will adjust for any possible imbalances in these baseline covariates among FCGs that occur due to the randomized assignment to the intervention. This analysis approach will hold for those endpoints collected only at two time points (i.e., baseline and 8 weeks).

Aim 3. Descriptive statistics, including mean, median, and standard deviation (minimum and maximum) for the utilization measures (i.e., hospitalizations and ED visits) will be provided. Considering the count nature of the utilizations, and to also account for any potential differences between the baseline characteristics of the care recipients in the two study arms, we will use Poisson regression to model various utilization outcomes.¹⁸² We expect that the gains (decreased healthcare utilization and costs) will be sustained beyond the enrollment period. Therefore, both descriptive and multivariable-adjusted measures will be estimated for the intervention period and the subsequent months post-intervention. A limitation of this economic approach will be the memory recall of the FCGs. We will provide a worksheet similar to Table 2 for all participants to help them track services and costs.

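### No eligibility criterion requires an expected discharge home, so dyads outside the hospital-to-home question can be randomized and stay in the intention-to-treat comparison

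*Combined protocol and SAP*

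**What the plan says.** Under Sample – Target population, an adult care recipient at a study hospital "who receives an in-hospital palliative care consult and lives in Minnesota, Iowa or Wisconsin will be invited to participate". The FCG criterion adds geography: the person "lives in a Minnesota, Iowa or Wisconsin county that is designated as medically underserved or rural will be invited to participate". The exclusions concern residence in Rochester, ventricular assist devices, chronic pain, home infusion pain pumps and active addiction. Neither list mentions discharge destination. The same section opens with "Our target population is community-dwelling adult FCGs providing care to a loved one who has a serious life-limiting condition", which places the FCG in the community and says nothing about where the patient is going.

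Other sections have a return home in view:

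- Specific Aims, Aim 1 asks about outcomes "for FCGs as the care recipient moves from hospital care to home".
- The Theoretical Framework names the patient's move from hospital to home as one of its two transitions.
- Part 2 of the intervention is headed as an at-home component.
- Sample Size and Power Calculations supports accrual with patients "seen by the palliative care consulting service in both 2014 and in 2015 and discharged home to the major catchment area".

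The time windows use a different event. Research Design says "the intervention period will continue for 8 weeks after care recipients are discharged from the hospital", and the Analytical Plan sets assessments "at baseline, 2 weeks, and 8 weeks post patient discharge". Both need a hospital discharge, to any destination.

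Consent and randomization take place during the hospital stay. Intention to treat is the principal analysis.

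**The concern.** As written, a coordinator may enroll the FCG of a patient who is going straight to a nursing or inpatient hospice facility, or who is expected to die in hospital. Both patients are adults with a consult and an address in the three states. Randomization comes before discharge, so only a screening rule could keep such dyads out, and none is written.

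The possibility is realistic. Preliminary Studies, Study #2 reports that patients first seen by palliative care in hospital were late in their illness, and the intervention section itself foresees facility placement and death.

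Two things are at stake. The first is interpretation: the estimate would mix FCGs managing a return home with FCGs for whom none was expected, and the accrual estimate describes a narrower group than the criteria admit. The second is sensitivity: if the intervention does less for the second group, the average difference shrinks.

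**Working it through.** **Inputs.** From Sample Size and Power Calculations: 100 evaluable FCGs per group, effect size 0.487 (SD 1), two-sided two-sample t-test, alpha 0.01, stated power 80%, attrition about 30%, recruitment of 500 per group, 8 per month for 36 months. Assumed, because the documents do not give them: the share *q* of evaluable FCGs whose patient does not go home (10%, 20%, 30%, the same in both arms), the fraction *r* of the effect kept in that share (0 or one half), and an unchanged SD.

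**Step 1: the plan's own figure.** Power comes from the noncentral t distribution with 2n − 2 degrees of freedom and noncentrality d × √(n/2). For n = 100 and d = 0.487, the noncentrality is 0.487 × √50 = 3.44 and power is 79.9% (80.7% by the normal approximation). The stated 80% is reproduced.

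**Step 2: which sample size applies.** 100 / 0.70 = 143 per group to recruit. The stated rate gives 8 × 36 = 288 in total, or 144 per group, which agrees. The stated 500 per group is 1,000 in total, which would take 1,000 / 8 = 125 months. After 30% attrition, 500 leaves 350 per group. Both sizes are carried forward because the text supports each.

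**Step 3: dilution.** The average effect is d(q) = 0.487 × [1 − q(1 − r)].

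| Assumed share q | Effect, r = 0 | Power, n = 100 | Power, n = 350 | Effect, r = ½ | Power, n = 100 |
|---|---|---|---|---|---|
| 10% | 0.438 | 69.1% | 99.9% | 0.463 | 74.8% |
| 20% | 0.390 | 56.2% | 99.5% | 0.438 | 69.1% |
| 30% | 0.341 | 42.6% | 97.3% | 0.414 | 62.8% |

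With r = 0, keeping 80% power would need 124, 156 or 203 evaluable per group.

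**Step 4: the time origin.** Discharge to a facility is still a hospital discharge, so it starts the 8-week intervention, the 2- and 8-week assessments and the monthly cost calls. Death before discharge does not. For that case, Variables and Their Measurements has Aims 1 and 2 outcomes collected about two weeks after death. A baseline score and that one score give a slope if actual dates are used, since a least-squares slope does not depend on where time zero is placed. The rule does not say which time scale to use, and it does not cover the Aim 3 cost calls.

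**The case against.** The strongest reply is that the FCG, not the patient, receives the intervention. No intervention activities are planned for care recipients. Video visits reach the FCG on a study tablet or the FCG's own device, wherever the patient is. Pre-discharge visits happen regardless of destination. Support continues through the 8 weeks after facility placement or death, and Appendix A provides extra contacts for hospice transfer, nursing home placement and death. Also, the FCG must be the primary informal caregiver, so it is not clear that the FCG of an existing facility resident would qualify. Coordinators may also ask about destination in practice.

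Much of this stands. A reader might infer that every outcome clock assumes a discharge home, that these FCGs cannot receive the intervention, or that power falls to 43%. The documents support none of these. The clocks run from any hospital discharge. The FCG still receives most of the support. The 43% combines an assumed 30% share, zero effect and the smaller sample size. FCGs of patients who die in hospital and have no post-baseline score would leave the analysis as attrition and would not dilute it.

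The reply does not remove the gap in the criteria. The placement and death provisions deal with events during the 8 weeks. They do not say whether a dyad with no expected return home belongs in a trial of the move home, and unwritten screening may differ among three hospitals.

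**Conclusion.** The point holds as a mismatch between who may be enrolled and the question asked. It follows from the text alone and needs no assumption about numbers. Dilution is possible but of unknown size. At 100 evaluable per group and assumed shares of 10% to 30%, power would lie between 69% and 43% with no effect in those dyads, and between 75% and 63% with half the effect. At 350 evaluable per group it would be at least 97% even with no effect, and the problem would then be interpretation only. Which case applies depends on resolving the conflict between 500 per group and 288 in total. The missing time origin is confined to death before discharge and is already partly covered for Aims 1 and 2.

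**What to change.** 1. Add to both inclusion lists, to be applied before randomization: *at consent, the care team or the medical record indicates that the care recipient is expected to be discharged home.*
2. Keep under intention to treat any dyad whose destination changes after randomization.
3. For a patient who dies before discharge, compute the slope from an origin that every dyad has, such as the randomization or baseline date, and state what happens to the cost calls.
4. Report actual destination by arm.
5. Reconcile the 500 per group with the stated recruitment rate and period.

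If the sponsor does intend to include all destinations, the plan should say so, record the expected destination at baseline, and add a sensitivity analysis by that pre-randomization variable.

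The cost is one screening item and an amendment. Somewhat fewer patients will pass screening. Because enrollment is tied to the first palliative consult, the expected destination may still be uncertain for some. The accrual estimate need not change, since it already counts only patients discharged home.

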A study nurse will develop an individualized FCG plan of care based on their assessment of FCG risks, needs, strengths, and preferences.¹⁵⁰ A unique plan of care to support FCGs includes: (1) a wellness plan to meet their own self-care (preventive and health-related physical and emotional wellness needs) and concerns during the transition period and (2) help for the FCG to meet the care recipient's needs. FCG Readiness Plans are key components of the FCG plan of care providing anticipatory guidance to address self-care needs and to meet common symptom management challenges for use by FCGs. The nurse will assist the FCG in implementing the plan of care and refine the plan of care to accommodate changing caregiving needs throughout the 8-week intervention through FCG advocacy, teaching, guidance, and counseling through in-person visits (during the hospital stay), and video visits and phone contacts at home. A copy of the individualized self-care plan will be provided to the FCG at the end of the intervention. [name] (Co-I) contributes the necessary expertise to oversee and train the study nurses in the TPC for FCGs intervention.

The TPC for FCG intervention will be provided by experienced, certified palliative care registered nurses. Review and recommendations of plans of care will be provided weekly and more often as needed by a study palliative care team (physician, pharmacist and social worker). Team meetings will focus collectively on identifying and meeting the unique caregiving and self-care needs of each FCG incorporating tenets of both transitional care and palliative care (Figure 2). Review and updates of the plans of care will be conducted with the FCG and other clinicians on the study team to meet mutually agreed and attainable goals.

Part 1: Pre-discharge intervention. The study nurse will make the first pre-discharge I visit with the FCG within 24 hours of study enrollment either in person or via video and every other day visits with the FCG during the remainder of the care recipient's hospital stay. The study nurse will have

Figure 2. Technology-Enhanced Transitional Palliative Care for Family Caregivers
Intervention Objectives

Caregiving in Palliative Care ^{103,108}	Caregiving in Transitional Care ^{18,143,149}	
1. Education on palliative care 2. Self-care for the caregiver a. Balancing family, self, and caregiving responsibilities b. Sleep and rest c. Accepting help 3. Education on role of caregiver in palliative care context 4. Strategies to respond to care recipient physical symptoms and emotional issues 5. Goal setting and problem solving 6. Advance care planning	1. Education regarding care recipient medications, administration, and side effects 2. Discuss importance of follow-up with primary care, specialty providers 3. Education regarding indications of changes in care recipient condition and how to respond 4. Follow-up visit/Reconnect to primary care provider 5. Integrated care plan with health & community services 6. Communicating with healthcare providers	
Timeframe of Activities		
Each Hospital Day	Post-Discharge/Community based Visits	
APN daily interaction including transition planning with FCG	Weeks 1-4 Minimum of 2 virtual visits/week by APN with FCG, phone calls as needed	Weeks 5-8 Minimum of 1 virtual visit/week by APN with FCG, phone calls as needed

access to all baseline data collected to assist with assessment and care planning (See Table 1 below for variables and measures). During the pre-discharge visits the nurse will: (1) assess the FCG's physical and emotional self-care needs, including the involvement of secondary caregivers and/or formal service providers to support the FCG and develop a FCG wellness plan; (2) assess the FCG's knowledge and skills for skillful caregiving; (3) begin transitional care planning by working with the FCG, the palliative care consulting service and acute care staff, and local community service providers; and (4) develop individualized FCG Readiness Plans (adapted from Hospice & Palliative Nurses Association and AARP materials)^{2,117} to anticipate caregiving needs that may arise when they return home. On the day of care recipient's discharge, the nurse will confirm the FCG's understanding of caregiving needs, physical and emotional readiness for caregiving, and confirm that plans for FCG self-care and respite are in place.

Part 2: At home technology-enhanced intervention. A minimum of weekly video visits will occur during Part 2 of the study. The first video visit by the nurse with the FCG will occur within 24-48 hours of hospital discharge. During visits the nurse will: (1) Provide ongoing education, guidance, and support to the FCG to develop self-care and caregiving skills; (2) Coordinate the implementation of the community-based aspects of the transitional care plan to address the FCG's as well as the patient's needs; (3) reaffirm and provide education and anticipatory guidance for the use of individualized FCG Readiness Plans for common care recipient symptoms such as pain, breathlessness, anxiety, etc.; (4) if requested, collaborate through active dialog with the local community resources included in the transition plan; (5) if requested, collaborate with the primary care provider/specialty providers related to goals of care; (6) coach the FCG in preparation for care recipient/provider office visits; and based on her continuing assessments; and (7) provide additional video visits/phone calls to support the FCG. Palliative and transitional care intervention objectives and activities are listed in Figure 2. Frequency type and length of contacts will be documented to quantify the dose effect of the intervention.

Video visits will be accomplished via the Zoom application using the equipment of choice by the FCG: a 3G-enabled iPad (provided by the study) or their own Smartphone or personal computer enabled with a camera for video visits. Any required training on the equipment and software will be conducted by the study coordinator in person or over the phone during Part 1 of the intervention with additional 24/7 technical support provided by the study coordinator and the IT solutions contractor (Caryl Technologies, LLC) during Part 2.

The intervention will continue for the FCGs during the 8-week period. Based on our prior experience with the FCG population, it is possible that the care recipient may be placed in a long-term nursing facility or die during the 8-week study period. In the case of the death of the care recipient, bereavement support (phone calls, video visits, and written educational materials) for the FCG will be provided for the duration of the 8-week intervention interval.

Control group: Usual care condition

The FCGs randomized to the control group will receive a phone call by a member of the study team reminding them of the study and the next scheduled data collection date. This call will account for the nonspecific conditions of expectancy, social support, and attention considered necessary to generate placebo effects.¹⁵¹ If concerns are identified during the attention control interaction between FCGs and study personnel, the FCGs will be advised to call their primary care provider. Control group care recipients will receive consult visits by the palliative care team while hospitalized, usual hospital discharge planning, and primary and specialty care in the community after hospital discharge. Services received by the FCGs will be collated and considered for analysis as confounding factors. We do not anticipate care recipients will participate in any study activities.

Study procedures

Study Preparation and Monitoring. Following IRB approval, the study coordinators and clinician members of the research team will be educated on the purpose of this study, as well as trained in all study procedures by the investigators; training will occur at study initiation and at subsequent quarterly reviews of study procedures.

Intervention Fidelity. The investigators will ensure that all study personnel are delivering the intervention according to the study procedure manual through weekly supervision/monitoring during the first month and monthly thereafter. We will ask caregivers if we can record their video visit for fidelity monitoring purposes. The information would stay internal and the caregivers would be given the opportunity to decline being recorded. An intervention guide will be developed to help assure fidelity to the protocol. To guarantee intervention fidelity, Investigators will audit the first 6 intervention interactions and evaluate with a detailed checklist; 100% adherence is the expectation. Any inconsistencies or deviations from the protocol will be addressed with the study team immediately. To monitor fidelity over the course of the study, [name], [name] and [name] will use a check list to audit at least two intervention interactions for each FCG per study quarter. Challenges to intervention fidelity and how they will be resolved will be discussed with the intervention nurses during quarterly meetings. Review of study procedures and retraining of the intervention nurses and on-call palliative care staff will be done by the investigators, as needed.

Scientific Rigor and Transparency. Attention to scientific rigor and transparency is demonstrated by our plan to use methods to minimize bias and limit threats to internal and external validity. We will accomplish this by using the following: (1) a theoretical framework to guide development of the intervention; (2) validated measures specifically designed to evaluate caregiving and palliative care outcomes; (3) a clear and reproducible description of the intervention components and approach; (4) clearly outlined methods to evaluate fidelity to the intervention; (5) plans for exploring retention of participants during the intervention and data collection phase and determining factors that promote and/or hinder ongoing study participation; and (6) an inclusive sample to produce results that can be generalized to men and women.

Authentication of key biological and/or chemical resources. Findings regarding sex differences in FCG outcomes ^{9,152} have not been reported, although the majority of FCGs are female.¹⁵³ Based on the unequal sex distributions in other studies of FCGs,¹⁵⁴⁻¹⁵⁶ we anticipate the enrollment of FCG female participants will be greater than males. We have no evidence to suggest that the sex distribution of FCGs will impact our outcomes.

Variables and Their Measurements

Copies of instruments we will use are found in Appendix B, including core data elements for caregiving research suggested by the Palliative Care Research Cooperative Group.¹²⁹

Table 1 summarizes the concepts, variables and measures, and timing of data collection. Data, including sample characteristics (age, sex, race/ethnicity, marital status, education, how long the FCG has been providing care to the care recipient, any computer/Smartphone experience and availability) and questionnaires, will be collected by a study coordinator from all enrolled participants after obtaining consent (baseline) via in-person interviews prior to the care recipients' hospital discharge.

Self-reported data will be obtained by computer-assisted interviews, telephone or mailed questionnaires, based on FCGs preferences, from all FCGs at 2 weeks, at the end of the intervention period (Aims 1 and 2) and at 6 months (Aim 2). If FCGs choose to complete questionnaires independently, they will have the choice of receiving a packet by mail or a link to complete questionnaire electronically via REDCap. If any FCG would like assistance completing the questionnaires, the study coordinator will provide assistance. Given the complexity of cost data, participants will be telephoned monthly for 6 months post-hospital discharge for cost data collection needed to address Aim 3.

If the care recipient dies, we will collect Aims 1 and 2 outcomes data from the FCG approximately 2 weeks later, given that grieving family members' distress and satisfaction with care should be more stable 2 weeks after their loved one's death.^{157,158}

In order to assure the safety of participants, the intervention nurse or study social worker will follow up by phone with all participants, regardless of, who report a score of >10 on depressive symptoms on any questionnaire or if an intervention or control caregiver reports via phone, survey or email information that raises the concern for elder mistreatment or abuse about family or

interpersonal conflict with potential violence or risk for self-neglect. Standard best practice protocols on assessing depression risk and self-harm will be followed. These include:

- a. General and specific screening tools about neglect or mistreatment will be completed

- a) With any suspicion of risk for self-harm, violence, or safety, the person with the closest knowledge (who talked or visited with the care recipient or caregiver) immediately contacts MN, WI or IA Adult Protective Services.
- b) Police will also be contacted if there is an imminent or immediate threats
- c) If intervention nurse or study social worker determine no suspicion for harm, coping skills and resources are discussed and when necessary, referral to palliative care/hospice team social worker.
- d) All conversations and decisions are documented into study records.

Table 1. Framework concepts, variables, timing, and estimated burden

Concepts	Variables and Measures	Timepoints	Estimated Burden
Sample Characteristics			
	Age, gender, race/ethnicity, marital status, education, relationship of FCG to care recipient, how long the FCG has been providing care to the care recipient, any computer/Smartphone experience and availability, diagnoses, medications,	Baseline	2-6 minutes
Properties of the Transition			
	Mutuality, ¹³⁴ Single items for relationship of FCG/care recipient; Caregiving demand ¹²⁹	Baseline	2-6 minutes
Transition Conditions (Facilitators or Barriers)			
Characteristics	Spiritual/Religious beliefs, ¹²⁸ Time available for caregiving (FCG Responsibilities & Demands), ¹²⁹ Decision making preference, ¹³⁰ Health literacy, ¹³¹ Income (single items), FCG Support Needs, ¹³² Hospital Discharge Readiness, ¹³³ FCG Personal Health Problems ¹²⁹	Baseline	5-12 minutes
Patterns of Response (Outcomes)			
Aim 1	Preparedness for caregiving, ¹³⁴ Communication skills, ¹³⁵ Satisfaction with care - CG-PACIC ^{136,137}	Baseline, 2, & 8 weeks	6-10 minutes
Aim 2	Quality of Life (CG QOL Scale-Cancer), ^{9,138} Coping, ¹³⁹ Depression, ¹⁴⁰ Burden (Bakas Caregiving Outcomes Scale), ¹⁵⁹ Patient Outcome Scale-Carer ¹⁶⁰ ,	Baseline, 2, & 8 weeks	17-20 minutes
Aim 2	Depression, ¹⁴⁰ Burden (Bakas Caregiving Outcomes Scale), ¹⁵⁹ Positive Aspects of Care (6 months only); open-ended study satisfaction	6 months	6-10 minutes
Aim 3	Healthcare Utilization and Cost (Ambulatory and Home Care Record)	Monthly, 6 months	30 minutes

Properties of the transition. Guided by the theoretical framework for the study, measures of properties of the transition include the quality of the FCG/care recipient relationship (Assessment of Mutuality^{121,134,161-163}) and caregiver demand (hours of caregiving and length of time caregiving¹²⁹). Variables related to the properties of the transition serve as control variables or will be considered as covariates in the analysis.

Transition conditions (facilitators and barriers). Measures of facilitators/barriers also serve as control variables and include spiritual/religious beliefs,¹²⁸ time available for caregiving (due to other FCG responsibilities and demands),¹²⁹ decision making preferences,¹³⁰ health literacy,¹³¹ income, FCG support needs,¹³² readiness for hospital discharge¹³³ (measured at hospital discharge), and FCG personal health problems (if any).¹²⁹

Aim 1: Evaluate the effect of a technology-enhanced TPC care model on caregiving preparedness, communication with clinicians, and satisfaction with care for FCGs.

1. Preparedness for caregiving. The Preparedness for Caregiving Scale^{134,161,163} captures how well FCGs feel they are prepared for the multiple aspects of the caregiving role, using a 4-point response set ranging from 0 ("not at all") to 4 ("very well"). A mean score is calculated; higher scores indicate greater preparation for caregiving.¹⁶³ Cronbach alphas of 0.88-0.93 are reported.¹⁶³

2. Communication skills. The Communication with Physicians scale¹⁶⁴ will be used to measure the communication skills of the FCG. Originally designed for chronic disease self-management behavior, the scale has 3 questions targeting how often the FCG prepares a list of questions for the doctor, asks questions, and discusses personal problems across a 6-point response set ranging from “never” to “always.” Scores range from 0-5 with higher scores indicating better communication. Internal consistency and test-retest reliability coefficients are good (0.73, 0.89, respectfully).¹⁶⁴
3. Satisfaction with care. A modified version of the Patient Assessment of Chronic Illness Care (PACIC) will be used to obtain FCG perceptions of the quality of chronic illness care received by the care recipient, as used by Wolff and colleagues.¹³⁷ The PACIC was originally developed to measure patients’ perspectives of the care they had received for their chronic illness, based on best practices as described in the Chronic Care Model.¹⁶⁵ The PACIC consists of 20 questions with 5 subscales: (1) activation, (2) delivery system design, (3) collaborative goal setting, (4) problem-solving, and (5) follow-up/coordination.¹⁶⁵ Scoring is a total mean score and a mean score for each subscale. Internal consistency (Cronbach alpha) for the overall score is reported as 0.96.¹⁶⁵⁻¹⁶⁷

Aim 2: Evaluate the effect of technology-enhanced TPC on FCGs’ quality of life, burden, coping, and depression.

1. Quality of life. The Caregiver Quality of Life Scale – Cancer (CQOL-C) will be used to measure FCGs’ quality of life. The CQOL-C is a 35-item self-report measure of the impact on the caregiver’s physical, emotional and spiritual well-being and on the relationship with the care recipient.¹³⁸ Scores range from 0-140; higher scores indicate worse quality of life. Cronbach alpha of 0.91 is reported in cancer and palliative care caregivers.^{9,168}
2. Burden. The Bakas Caregiving Outcomes Scale-Revised (BCOS-R) will be used to measure the burden placed on FCGs in caring for their loved ones. The BCOS-R contains 15 items that measure changes as indicators of the effect of caregiving on FCGs’ lives.¹⁶⁹ The response set uses a 7-point Likert scale that ranges from “changed for the worst” to “changed for the best.” Higher scores indicate more positive caregiver outcomes.¹⁶⁸ Cronbach alphas range from 0.81 to 0.90.¹⁵⁹
